Hypersensitivity) or Placebo administered intralesionally in the largest common

wart

Cohort 2: 0.5 mL of CANDIN or Placebo administered intralesionally in the

largest common wart

Cohort 3: 0.3 mL of CANDIN or Placebo administered intralesionally in up to 4

warts at the same visit (up to 1.2 mL total injected volume)

Population: Approximately 156, male or female subjects aged 18 to 65, with 3 to 20 common

warts on hands, feet (excluding soles), limbs and/or trunk will be included in this

study

Number of Sites: Approximately 15 centers in USA will participate in this study

Study Duration: Subjects will be treated for a maximum of 29 weeks followed by a 16-week

observation period for a total of 45 weeks, excluding the 4-week screening period.

Hypothesis: The null hypothesis for this study is that the CANDIN treatments are not

significantly different from placebo under these experimental conditions

Objectives:

The primary objective is to assess the efficacy of CANDIN treatment in subjects with common warts by evaluating the number and proportion of subjects with the primary injected wart(s) completely resolved.

The secondary objectives are:

1. To assess the safety and tolerability of CANDIN

Nielsen- CFW-2D Protocol Final version 5.0: 06Dec2016

Endpoints:

[figure not shown]
Primary Endpoint:

 The number and proportion of subjects with the primary injected wart(s) completely resolved at any treatment or Follow-up Visit

Secondary Endpoints:

1. Incidence of site injection Adverse Event (AE) for all subjects and Treatment-Emergent Adverse Event (TEAE) for subjects randomized to CANDIN

Overall Study Design

This is a placebo-controlled, double-blind (subject, Investigator, and site staff with the exception of unblinded dedicated staff to handle study medication), phase 2a study with 3 dose cohorts, randomized (concealed) to CANDIN or placebo (3:1). Main study will be up to 20 weeks (10 doses administered every other week) or until a subject has complete resolution of all injectable common warts. Subjects who cannot tolerate dosing every 2 weeks due to a local tolerance issue may be injected at 3-week intervals for up to 10 doses, increasing the length of the study to 29 weeks. Subjects will be followed for 4 months after final injection(s) for evidence of new or reoccurring warts and for safety evaluation.

Inclusion Criteria

Subjects may be eligible if they meet all the following inclusion criteria at the Screening and Baseline Visits unless specified otherwise:

- 1. Men or women between the ages of 18 and 65 years inclusively at time of consent
- 2. Subjects presenting with 3 to 20 injectable common warts (verruca vulgaris) for at least 12 weeks at the time of the Baseline Visit
- 3. Subject's common warts for injection must measure between 3 and 20 mm at Baseline Visit and be located on hands, feet (excluding soles), limbs, and/or trunk. Flat, plantar, facial, periungual, genital warts or warts in region of pre-existing inflammatory condition are excluded from injection
- 4. Subjects enrolled into Cohort 3 must have common warts for injection in at least 2 different anatomical regions defined as: left arm, right arm, left hand, right hand, left leg, right leg, left foot (excluding sole), right foot (excluding sole) and torso
- 5. Subject, male or female is willing to use effective contraceptive method for at least 30 days

Confidential and proprietary. Permission should be obtained before any reproduction.

before the Baseline Visit and at least 30 days after the last study drug administration unless not of childbearing potential as defined as post-menopausal for at least 2 years (females) or surgically sterile (tubal ligation, oophorectomy, or hysterectomy for females, and vasectomy for males). The only contraceptive use exceptions would be individuals in exclusive same sex partnerships and individuals who agree to remain non-sexually active for the duration of the study. Acceptable contraceptive methods for subjects include:

- a. Barrier methods, such as condom, sponge or diaphragm, combined with spermicide in foam, gel or cream;
- b. Hormonal contraception (oral, intramuscular, implant or transdermal which includes Depo-Provera, Evra and Nuvaring);
- c. Intrauterine device (IUD)

Female subjects of childbearing potential in a same sex partnership or who are abstinent will still receive pregnancy test as outlined in Appendix A.

6. Mentally and legally capable of giving informed consent prior to any study related procedures

Exclusion Criteria

Subjects will not be eligible if they meet any of the following criteria at the Screening or Baseline Visits unless specified otherwise:

- Presence of systemic or localized diseases, conditions, or medications that could interfere with assessment of safety and efficacy or that compromise immune function including psoriasis
- 2. Subject has been diagnosed with diabetes mellitus
- 3. Subject has a history of keloid formation
- Injectable common wart(s) located in areas with existing dermatologic conditions (such as psoriasis) or with an underlying inflammatory conditions (such as arthritic joints), or tattoos or implants/piercing/hardware or marking that may conceal responses or reactions are excluded from injection
- 5. Existing/planned pregnancy, childbirth in the past six months prior to the Baseline Visit, or breast feeding, or plan on donating eggs or sperm during the study and in the month following the last injection
- Treatment of warts with liquid nitrogen, carbon dioxide, electrodessication, laser, surgery, simple occlusion (e.g. duct tape), salicylic or related acids, OTC treatments, cantharidin, or other treatments (other than immunotherapy or those intended to stimulate immune response) within 4 weeks of the Baseline Visit
- Treatment with immunotherapy (DPCP, DNCB or other), imiquimod, 5-fluorouracil, bleomycin, podophyllin or any other wart immunotherapy or treatment designed to stimulate immune response (except for treatments already listed in exclusion criterion 6) within 12 weeks of the Baseline Visit
- Recalcitrant warts defined as those not successfully treated by five or more treatments

(excluding OTC treatments).

- 9. Abnormal (low < 5 mm or high >25 mm) baseline result to the Delayed Type Hypersensitivity (DTH) test
- 10. Subject has a condition or treatment resulting in being immunocompromised
- 11. Systemic treatment (such as oral or injected) with cimetidine, zinc supplements at a dose higher than 20 mg of elemental zinc daily or an immunosuppressive drug (such as: azathioprine, 6-mercaptopurine, methotrexate, infliximab, adalimumab, etanercept, systemic steroids, etc.) within 12 weeks of the Baseline Visit. Note that subjects should not discontinue use of immunosuppressive therapy for the purpose of entering the study as the underlying conditions also could interfere with the study.
- 12. Subject has used any investigational agent within 30 days prior to the Baseline Visit or within 5 half-lives of that investigational agent prior to the Baseline Visit (whichever is longer)
- 13. Previous treatment of warts with any type of intralesional injection with candida extract (including CANDIN)

Statistical Considerations

The primary endpoint is the number and proportion of subjects with complete resolution of the primary injected wart(s). The proportion of subjects with the complete resolution of treated warts will be compared among all treatment groups using the Cochran-Mantel-Haenszel test with a stratification factor of single versus multiple anatomical regions. In addition each active treatment will be compared with the pooled placebo in a similar manner. There will be no adjustment of the type 1 error for multiple comparisons.

Sample Size Determination

A total of approximately 156 subjects will be enrolled into the study with approximately 52 subjects in each active treatment arm and the pooled placebo group. One assumes that the pooled placebo arm has a 24% complete resolution rate and one of the active treatment arms has a complete resolution rate of 70%. The statistical comparison between each active treatment and the pooled placebo will be conducted at the 0.05 significance level. It is assumed that at least 90% of the subjects will either complete the study or reach complete resolution. A sample size of approximately 52 per arm will provide 94% power to detect a statistically significant difference between an active treatment and the pooled placebo. The assumed Nielsen- CFW-2D

Protocol Final version 5.0: 06Dec2016

Nielsen- CFW-2D Protocol Final version 5.0: 06Dec2016

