5 STUDY POPULATION

Approximately 156, male or female subjects aged 18 to 65 inclusively at the signature of consent with 3 to 20 common warts on hands, feet (excluding soles), limbs and/or trunk will be included in this study in order to complete with approximately 115 subjects. Drop-outs will not be replaced. Additional subjects may be added to ensure approximately 115 subject complete the study in the event an investigator or site discontinues participation in the study

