6 TREATMENT

6.1 Treatment Administered

Subjects who fulfill all the inclusion and none of the exclusion criteria may be accepted in the study. Each subject should read and sign an informed consent form prior to any screening procedures being performed. This study involves a comparison of an intralesional injection of CANDIN with an intralesional injection of placebo (unpreserved normal saline solution) in common warts. Subjects will receive one (Cohorts 1 and 2) or more (Cohort 3) intralesional injections every two weeks (14 +/- 2 days) at the region of the interdigitated base of wart (epidermal/dermal junction) for up to 20 weeks (a maximum of 10 doses per subject) or up to resolution of all injectable warts. Subjects who experience local tolerance issues when dosing is performed at 2-week intervals may be injected at 3-week intervals (21 +/- 2 days) also for a maximum of 10 doses per subject.

Subjects will be included in three cohorts as follows:

- 1. Cohort 1: Approximately 52 subjects will receive 0.3 mL of either CANDIN (n=39) or placebo (n=13) intralesionally in the largest common wart (primary) every second week (14 +/- 2 days) for a maximum of 10 injections. If the primary common wart exhibits a complete response, the second largest injectable common wart of all anatomical regions will be injected with CANDIN at the same dose. If the second largest common wart exhibits a complete response, the third largest of all anatomical regions will be injected. If an injected wart recurs after exhibiting a complete response, it will be re-injected instead of the non-primary injected wart that was injected at the previous visit. This injection strategy will be repeated for a maximum of 10 injections per subject or until all injectable common warts exhibit a complete response, if it occurs before all 10 injections are used.
- 2. **Cohort 2:** Approximately 52 subjects will receive 0.5 mL of either CANDIN (n=39) or placebo (n=13) intralesionally in the largest common wart every second week (14 +/- 2 days) for a maximum of 10 injections. If the primary common wart exhibits a complete

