2.3 Exploratory Objectives

3 STUDY OVERVIEW

3.1 Study Design

This is a placebo-controlled, double-blind (subject, Investigator, and site staff with the exception of unblinded dedicated staff to handle study medication), multi-center, Phase IIa study with 3 dose cohorts, randomized to Candin or placebo in a 3:1 ratio. The main study will be up to 20 weeks (10 doses administered every other week) or until a subject has complete resolution of all injected common warts. Subjects who cannot tolerate dosing every 2 weeks (14 ± 2 days) due to a local tolerance issue may be injected at 3-week (21 ± 2 days) intervals for up to 10 doses, increasing the length of the study to 29 weeks. Subjects will be followed for 4 months after final injection(s) for evidence of new or reoccurring warts and for safety evaluation.

Approximately 156 (male or female) subjects aged 18 to 65 inclusive at the date of consent, with 3 to 20 common warts on hands, feet (excluding soles), limbs, and/or trunk will be included in this study. It is assumed that approximately 80% of the subjects will either complete the study or reach complete resolution. Drop-outs will not be replaced. Refer to Section 9 for sample size and power of the study.

Subjects will be included in three cohorts as follows:

Cohort 1: Approximately fifty-two subjects will receive 0.3 mL of either Candin (n=39) or placebo (n=13) intralesionally in the largest (primary) common wart every second week (14 ± 2 days) for a maximum of 10 injections. If the primary common wart exhibits a complete response, the second largest injectable common wart of all anatomical regions will be injected with the randomized study medication at the same dose. If the second largest common wart exhibits a complete response, the third largest wart of all anatomical regions will be injected. If an injected wart recurs after exhibiting a complete response, it will be re-injected instead of the non-primary injected wart that was injected at the previous visit. This injection strategy will be repeated for a maximum of 10 injections per subject, or until all injectable

common warts exhibits a complete response if that occurs before all 10 injections are used.

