Cohort 2: Approximately fifty-two subjects will receive 0.5 mL of either Candin (n=39) or placebo (n=13) intralesionally in the largest (primary) common wart every second week $(14 \pm 2 \text{ days})$ for a maximum of 10 injections. The same procedures will be followed in the event of complete response or recurrence as described for Cohort 1.

Cohort 3: If the safety data from Cohort 2 support continuation of the study (defined as medical assessment of the first eight subjects of Cohort 2 completing three injections), approximately 52 subjects planned for Cohort 3 will receive either 0.3 mL/wart Candin (n=39) or placebo (n=13), with a total per visit not to exceed 1.2 mL. Subjects in Cohort 3 must have injectable common warts in at least 2 different anatomic regions. Candin or placebo will be injected under the largest (primary) wart per major anatomical region (left or right; arm, hand, leg, foot excluding sole, or the torso) for a minimum of two and a maximum of four injections per visit, every second week (14 ± 2 days) for a maximum of 10 visits with injections. No more than one wart per anatomical region will be injected on any given visit. If any primary injected wart exhibits a complete response, the next largest injectable common wart will be injected with the randomized study medication at the same dose (maximum of 4 injections per visit), providing the new injectable wart is not within the same anatomical region as other currently injected warts. (If an injected wart recurs after exhibiting a complete response, it will be reinjected instead of the non-primary injected wart that was injected at the previous visit.) This injection strategy will be repeated for a maximum total of 10 injection visits per subject or until all injectable common warts exhibit a complete response, if it occurs before the end of the 10 injection visits.

Two Follow-up visits are included in the study to further assess the efficacy and safety of the study medication. Follow-up information will be obtained for subjects who discontinue their participation in the study. All procedures scheduled for during Follow-up Visit 1 and Follow-up Visit 2 should be completed for early termination subjects, as well as for those subjects who have complete resolution of all common warts prior to their Efficacy Evaluation visit (V13).

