3.3 Randomization Schedule and Blinding Procedures

This is a double-blind study defined as blinding of subjects, investigators, and site personnel not involved in study medication preparation and accountability. A concealed, centralized randomization list generated by an unblinded Sponsor representative will be used to assign the cohort and treatment to the subjects using an internet-based system. Randomization will be unbalanced (3:1) in favor of Candin. To maintain the blind, a qualified, unblinded person at each study site will prepare the syringes containing the medication (CANDIN or saline) independently from the Investigator performing the injection and making the evaluations. Subjects will be randomly assigned to cohorts first, and then to treatment, according to Table 2.

Randomization Number of Number of Number of Ratio between Randomized Randomized Subjects in **Anatomical Regions Subjects** to Candin to Placebo **Cohorts within Cohorts** Stratum Cohort 1 = 3325 8 Single 66 1:1 Cohort 2 = 3325 8 Cohort 1 = 1914 5 5 Multiple 90 4:4:11 Cohort 2 = 1914 Cohort 3 = 52

Table 2. Randomization Structure by Stratum, Cohort, and Treatment

The first 16 subjects will be randomized (1:1) to Cohort 1 or 2 until medical assessment of the first eight subjects of Cohort 2 (6 on active and 2 on placebo) completing three injections supports continuation of the study to Cohort 3. Once medical assessment supported continuation of the study to Cohort 3, subsequent subjects with warts in at least 2 different anatomical regions will be randomized to Cohort 1, 2, or 3 in a ratio of 4:4:11 to ensure that the treatment assignment for the overall 156 subjects will approximately preserve the above randomization structure.

The treatment randomization assignments will be kept secured from the Investigator and/or blinded site staff in the unblinded pharmacy binder until the database is finalized and hard locked.

The investigational site will assign each subject a subject identifier number during screening that will be used on all subject documentation throughout the study. Numbers will be assigned in ascending order using Sponsor's numbering system.

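### The sample-size text counts 52 subjects per compared group where the design gives 39, and its 94% power and 90% retention do not fit the other stated figures

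*Protocol*

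**What the plan says.** The protocol synopsis, under Sample Size Determination, plans about 156 subjects with "approximately 52 subjects in each active treatment arm and the pooled placebo group". It assumes resolution rates of 24% on pooled placebo and 70% on an active arm, and tests each active arm against pooled placebo at 0.05. On retention it says "It is assumed that at least 90% of the subjects will either complete the study or reach complete resolution". It concludes: "A sample size of approximately 52 per arm will provide 94% power to detect a statistically significant difference".

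Protocol 6.1 describes Cohort 1 as "Approximately 52 subjects will receive 0.3 mL of either CANDIN (n=39) or placebo (n=13", with the same split for Cohorts 2 and 3. SAP 3.1 repeats these numbers, for example "approximately 52 subjects planned for Cohort 3 will receive either 0.3 mL/wart Candin (n=39) or placebo (n=13" for Cohort 3. SAP 7.1 names four treatment groups: pooled placebo and the three Candin cohorts.

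SAP 3.1 gives a different retention figure: "It is assumed that approximately 80% of the subjects will either complete the study or reach complete resolution". Protocol Section 5 recruits 156 "in order to complete with approximately 115 subjects".

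**The concern.** Three things do not fit together.

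- **Group size.** 52 in each of four groups exceeds the stated total, and it contradicts the 39 and 13 split.
- **Power.** A 46-point difference with about 50 subjects per group should give power close to 100%, so 94% looks wrong for the inputs beside it.
- **Retention.** The same quantity takes two values in the two documents.

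If the 52 is a slip, the protocol overstates every compared group by a third (52/39 = 1.33). A reader could not tell which group size, which loss and which test the 94% describes. It also has to be asked whether power is still adequate once the group size is corrected.

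**Working it through.** **Head count.** Inputs: 39 + 13 per cohort, three cohorts (Protocol 6.1, SAP 3.1).

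- Active arms: 39 each. Pooled placebo: 3 x 13 = 39. Total: 4 x 39 = 156, as stated.
- With 52 per group: 4 x 52 = 208, which is 52 more than planned.
- SAP Table 2 gives placebo counts of 8 and 8 in the single-region stratum and 5 and 5 for Cohorts 1 and 2 in the multiple-region stratum. The Cohort 3 split is not legible in the text available here. With the 13 from SAP 3.1, placebo is 8 + 8 + 5 + 5 + 13 = 39.

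**Power from the plan's own inputs.** Rates are 0.24 and 0.70, alpha is 0.05, and tests are two-sided (SAP 7.1.1). With n per arm and mean rate 0.47, the pooled-variance normal formula is

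power = Φ[(0.46 − 1.96·s0)/s1], where s0 = √(0.47 × 0.53 × 2/n) and s1 = √((0.24 × 0.76 + 0.70 × 0.30)/n).

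- n = 52: s0 = 0.0979, s1 = 0.0869, z = 3.09, power 99.9%.
- n = 39: s0 = 0.1130, s1 = 0.1003, z = 2.38, power 99.1%.

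The continuity-corrected version subtracts 1/n from 0.46. Fisher's exact test was enumerated in full.

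| n per arm | Basis | Pooled normal | Corrected | Fisher |
|---|---|---|---|---|
| 52 | as stated | 99.9% | 99.8% | 99.8% |
| 47 | 90% of 52 | 99.8% | 99.5% | 99.4% |
| 39 | actual design | 99.1% | 98.3% | 98.2% |
| 35 | 90% of 39 | 98.4% | 96.9% | 96.2% |
| 31 | 80% of 39 | 97.0% | 94.4% | 94.8% |

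The plan's 94% is not reproduced at 52 or 47 per arm. Variants do not help. With 52 per arm, a one-sided test gives over 99.9%, alpha of 0.05/3 gives 99.5%, and counting the lost 10% as failures gives 99.5%. At 52 per arm, 94% power would correspond to an active rate of about 57% (pooled) or 59% (corrected), not 70%.

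**Planned stratified test.** Cochran-Mantel-Haenszel power was simulated for the Table 2 strata, assuming the same response rates in both strata.

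| Contrast with pooled placebo | Active vs placebo by stratum | No loss | 90% retained | 80% retained |
|---|---|---|---|---|
| Cohort 1 or 2 | 25 vs 16 (single), 14 vs 23 (multiple) | 98.6% | 97.7% | 95.8% |
| Cohort 3 | 39 vs 23 (multiple only) | about 96% | 93.8% | 89.7% |

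Cohort 3 requires warts in at least two regions. The 16 single-region placebo subjects therefore contribute nothing to its stratified contrast, and 5 + 5 + 13 = 23 remain. For 39 vs 23 without loss, the three unstratified methods give 96.1%, 92.8% and 93.9%.

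**Retention.** 90% of 156 is 140; 80% is 125; 115/156 is 73.7%. The first two are values for one quantity. The 115 may be another quantity, because SAP 6.1 counts a subject as completing the study only after both follow-up visits.

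**The case against.** The strongest reply is that this is a cohort-for-arm labelling slip in a phase 2a study. The operational text has the correct 39 and 13, so nobody would be randomised wrongly. The stated power is lower than its inputs give, which errs on the cautious side. All of that stands, and it limits how serious the point is.

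A second reply is that the 94% may be sound but mislabelled: 39 per group with the SAP's 80% retention leaves 31, where corrected and Fisher power are 94.4% and 94.8%. That is plausible but cannot be confirmed. About 94% also appears elsewhere: 27 per arm pooled (94.6%), 30 per arm corrected or Fisher (93.6%), and 39 vs 23 by Fisher (93.9%). If the reading is right, the protocol's 52 and 90% are the figures in error, which supports the correction.

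Third, some text cannot be seen. The synopsis paragraph breaks off, and SAP Sections 8 and 9 show only headings. The SAP (February 2018) is later than protocol version 5.0 (December 2016), so an explained change from 90% to 80% cannot be excluded. A hidden assumption could account for the 94%. It could not make four groups of 52 add up to 156.

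Finally, 39 pooled placebo subjects depends on the cohorts looking comparable (Protocol 14.5), and SAP 7.1 pools Cohort 3 with the multiple-region subjects of Cohort 1 for the comparison of doses. Neither makes 52 the size of the groups described in the sample-size paragraph.

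**Conclusion.** The concern holds on all three parts. The group size is wrong as written: 39, not 52. The 94% does not follow from 52 per arm, 24% versus 70% and 90% retention, which give over 99%. The protocol and SAP assume different retention for the same quantity. How the 115 completers relate to it is unclear, but that is not a proven contradiction.

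Adequate power is not threatened for the unstratified comparison: 98.2-99.1% at 39 per arm, and 94.4-97.0% if 20% of subjects drop out of the analysis. The reduced-size rows probably overstate the loss, because SAP 5.4 keeps any treated subject with one post-baseline measurement of the primary wart(s). The margin is thinner for Cohort 3 in the stratified test: about 93-96% without loss, and about 90% if 20% are lost. These figures assume the planned rates, pooled placebo and, for the stratified test, equal rates across strata. The text should be corrected; the design need not change.

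**What to change.** 1. In the sample-size paragraph, state approximately 39 subjects in each active treatment arm and 39 in pooled placebo: 156 in total, 52 per cohort.
2. Restate power for 39 per group and name the test. For example, Fisher's exact test at two-sided 0.05 with 24% versus 70% gives about 98% without loss. Add the figure after the assumed loss. Because the planned test is stratified, a Cochran-Mantel-Haenszel figure is preferable.
3. Use one value for the finish-or-resolve assumption in both documents, and say how the 115 completers relate to it.
4. As a suggestion, note that the stratified Cohort 3 contrast rests on 39 versus about 23 placebo subjects.

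The cost is wording only. Enrolment, allocation and analysis stay as they are.
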